## 6.7. Patient Characteristics

A summary table will be generated for patient characteristics at study entry using all randomized patients. The following variables will be included but not limited to: age, age groups (<40 and ≥40 years, and <65 and ≥65 years), sex, country, race, height, weight, body mass index (BMI), BMI groups (<25, ≥25 to <30, ≥30 to <35, and ≥35 kg/m^2). For continuous variables, the following statistics will be provided: mean, SD, minimum, maximum, and median, and treatment groups will be compared using an analysis of variance (ANOVA) model with a term of treatment. For categorical variables, summary statistics will include sample size, frequency and percentage, and treatment groups will be compared using Fisher's exact test or Pearson's chi-square test. A listing of patient characteristics at study entry will be provided.

A similar summary of diabetes characteristics will also be generated. The following variables will be included but not limited to: duration of diabetes, the type of prandial insulin at study entry, the type of basal insulin therapy at study entry (including whether given once daily [QD] or twice-daily [BID]) and randomization, the type of pre-mix insulin at study entry, number of prandial injections at study entry (<3, ≥3), oral antihyperglycemic medication (OAM) use at study entry and randomization, prandial insulin dosing plan, HbA1c at study entry and baseline, HbA1c stratum (based on measurement at baseline), and fasting serum glucose at Visit 2 and baseline (based on mixed-meal tolerance test [MMTT]).

A listing of patients whose stratification factor value entered into the IWRS (for treatment group assignment) is different from the clinical database will also be provided.

For all randomized patients, the number and percentage of patients with historical conditions will be summarized by treatment group using Medical Dictionary for Regulatory Activities (MedDRA) PT (without regard to SOC), and the number and percentage of patients with preexisting conditions will also be summarized by treatment group using MedDRA PT (without regard to SOC). Historical conditions are conditions that end prior to informed consent and preexisting conditions are conditions that are still ongoing at informed consent. Events will be ordered by decreasing frequency. No statistical comparisons between treatment groups will be performed.

### 6.8. Treatment Compliance

No analysis for treatment compliance is planned for this study.

### 6.9. Important Protocol Deviations

Protocol deviations will be identified throughout the study. Important protocol deviations are defined as those deviations from the protocol likely to have a significant impact on the completeness, accuracy, and/or reliability of the study data or that may significantly affect a subject's rights, safety, or well-being.

CCI

The listing of important protocol deviations for all randomized patients during the entire study, with the indication of whether to be excluded from the PP population, will also be provided. CCI

### 6.10. Concomitant and Prior Therapy

Concomitant medication will be summarized and compared between treatment groups using Fisher's exact test for the Randomized Population during the treatment period. The percentages of patients receiving each concomitant medication will be summarized by treatment using PT nested within Anatomical Therapeutic Chemical (ATC) Level 3 code. Medications will be ordered by decreasing frequency within ATC level. Concomitant medication used during the lead-in period will also be summarized for the Enrolled Population.

A summary of previous diabetes therapies that were discontinued prior to informed consent will be generated for the Enrolled Population.

Total daily basal and total daily prandial insulin doses for the day prior to Visit 2 will be entered into the eCRF. The daily basal doses and individual prandial insulin doses (that is, morning meal, midday meal, evening meal, bedtime/snack/other) will be entered into eCRF after Visit 2. At a given visit, total daily basal insulin dose to be used for analysis will be calculated as the

mean of the total daily basal insulin doses on the 3 days prior to the visit date (or the days between the previous visit date and the current visit date if the number of days between the 2 visit dates is <3). Similarly, the dose for each meal will be calculated as the mean of the doses on the 3 days prior to the visit date (or the days between the previous visit date and the current visit date, whichever smaller). Total daily prandial insulin dose to be used for analysis will be calculated as the sum of the individual meal insulin doses. If either total daily basal insulin dose or total daily prandial insulin dose is missing, total daily insulin dose and prandial/total insulin dose ratio will be set as missing for analysis.

Total daily basal insulin dose, total daily prandial insulin dose, total insulin dose, and the ratio of prandial insulin dose to total insulin dose during the lead-in period will be summarized by visit for the Randomized Population. The actual and change from Visit 2 values will be compared between treatment groups using an MMRM model including the corresponding dose at Visit 2, treatment, strata (country, type of basal insulin during the lead-in period, the number of prandial doses at study entry and HbA1c stratum at baseline), visit, treatment-by-visit interaction in the model as fixed factors and patient as a random factor. The actual and change from Visit 2 at Visit 8 (LOCF) will be compared using ANCOVA model including the corresponding dose at Visit 2, treatment, strata (country, type of basal insulin during the lead-in period, the number of prandial doses at study entry and HbA1c stratum at baseline). Doses will be summarized in U and U/kg. Basal insulin dose will be summarized independently for glargine and degludec as well as combined.

Up to 3 OAMs (metformin, dipeptidyl peptidase-4 inhibitor [DPP-4] inhibitor, sodium-glucose co-transporter 2 [SGLT2] inhibitor, sulfonylurea, meglitinide and alpha-glucoside inhibitor) are allowed prior to the study, and up to 2 OAMs (metformin and SGLT2 inhibitor) are allowed during the lead-in and treatment periods. The proportion of patients who were treated with OAMs (by class of OAM) at each visit will be summarized and compared between treatment groups using Fisher's exact test. The number of OAMs per patient will also be summarized by treatment and by period: lead-in period (Visit 2 to Visit 8) and treatment period (Visit 8 to Visit 18).

## 6.11. Efficacy Analyses

### 6.11.1. Primary Outcome and Methodology

The primary objective of this study (H1) is to test the hypothesis that LY900014 is noninferior to insulin lispro on glycemic control (NIM=0.4% for HbA1c) in patients with T2D, when administered as prandial insulin (0 to 2 minutes prior to the meal), in combination with basal insulin for 26 weeks.

The primary efficacy comparison will be based on the contrast between LY900014 and insulin lispro at Week 26 (Visit 18) from the MMRM analysis of change from baseline in HbA1c including data collected from all randomized patients prior to permanent discontinuation of IP through Week 26. The model for the analysis of the primary efficacy endpoint of change from

baseline in HbA1c will include the fixed class effects of treatment, strata (country, type of basal insulin during the lead-in period, and number of prandial doses at study entry), visit, and treatment-by-visit interaction, as well as the continuous, fixed covariates of baseline value. An unstructured covariance structure will be used to model the within-patient errors. Significance tests will be based on LS means and Type III tests. If this analysis fails to converge, the following covariance structures will be tested in order:

- Toeplitz with heterogeneity
- autoregressive with heterogeneity
- compound symmetry with heterogeneous variances
- Toeplitz
- autoregressive
- compound symmetry without heterogeneous variances

The first covariance structure that converges will be used. The Kenward-Roger approximation will be used to estimate denominator degrees of freedom.

For both primary analysis approaches, LY900014 will be declared noninferior to insulin lispro if the upper limit of the 2-sided 95% CI for the LS mean difference in the change from baseline in HbA1c for LY900014 minus insulin lispro is below +0.4%.

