The primary efficacy comparison will be based on the contrast between LY900014 and insulin lispro at Week 26 (Visit 18) from the mixed-effect model repeated measure (MMRM) analysis of change from baseline in HbA1c, including data collected from all randomized patients prior to permanent discontinuation of IP through Week 26. If the upper limit of the 2-sided 95% confidence interval (CI) for the least squares (LS) mean difference in the change from baseline in HbA1c for LY900014 minus insulin lispro is below +0.4%, LY900014 will be declared non-inferior to insulin lispro. The model for this analysis will include the fixed class effects of treatment, strata (country, type of basal insulin, and number of prandial doses at entry), visit, and treatment-by-visit interaction, as well as the continuous, fixed covariate of baseline value.

A graphical approach (Bretz et al. 2011) for multiple comparisons will be used to strongly control the overall Type I error (2-sided alpha level of 0.05) for testing the treatment effect for the primary and the following multiplicity adjusted objectives: superiority of LY900014 compared with insulin lispro for 1-hour PPG excursion at Week 26, 2-hour PPG excursion at Week 26, and change from baseline to Week 26 in HbA1c.

An analysis of covariance (ANCOVA) model with strata (country, type of basal insulin, baseline HbA1c [$\leq 8.5\%$, $>8.5\%$], and number of prandial doses at entry), and treatment as fixed effects and baseline as a covariate will be used to analyze the 1-hour and 2-hour PPG excursions. However, if the percentage of the patients with missing MMTT data at baseline is higher than 15%, a constrained longitudinal data analysis model (Liu et al. 2009; Lu 2010) will be used instead. Analyses details will be documented in the statistical analysis plan (SAP).

Hypoglycemia rates will be summarized for periods of 30 days, 1 year, and 100 years (severe hypoglycemia only). The rate of severe hypoglycemia per 100 years will be compared between treatment groups using the empirical

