5.4. Scientific Rationale for Study Design

Study ITSE is a Phase 3 study to evaluate LY900014 compared to insulin lispro each in combination with basal insulin glargine or degludec in patients with T2D. The trial has 2 double-blind treatment groups, to allow comparison of LY900014 and insulin lispro when injected at the start of the meal. The 2:1 randomization ratio is to meet the regulatory requirement of China SDA.

The study is designed to compare HbA1c lowering as the primary endpoint, a measure of glycemic control accepted by health care providers and regulatory authorities as a validated measure of glycemic control over time and as the best marker for the development and progression of diabetes complications. The lead-in period consists of 8 weeks to allow for optimization of basal insulin dosing. The 26-week treatment period consists of a 12-week intensive titration period to optimize prandial insulin dosing followed by a 14-week maintenance period to ensure that the primary endpoint HbA1c reflects glycemic control on the patient's insulin regimen.

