10.3.3.2. Secondary Analyses

A graphical approach for multiple comparisons will be used to strongly control the overall Type I error (2-sided alpha level of 0.05) for testing the treatment effect for the primary and the following multiplicity adjusted objectives: superiority of LY900014 compared with insulin lispro for 1-hour PPG excursion at Week 26, 2-hour PPG excursion at Week 26, and change from baseline to Week 26 in HbA1c. The graphical testing scheme will be described in the SAP.

An ANCOVA model with strata (country, type of basal insulin, number of prandial doses at entry, and baseline HbA1c [$\leq 8.5\%$, $> 8.5\%$]), and treatment as fixed effects and baseline as a covariate will be used to analyze the 1-hour and 2-hour PPG excursions. However, if the percentage of the patients with missing MMTT data at baseline is higher than 15%, a constrained longitudinal data analysis model (Liu et al. 2009; Lu 2010) will be used instead. Analyses details will be documented in the SAP.

Superiority in change from baseline in HbA1c for LY900014 compared with insulin lispro will be determined from the analysis approaches outlined in Section 10.3.3.1.

Hemoglobin A1c and change from baseline in HbA1c at all time points will be analyzed by the same MMRM model used for the primary analysis..

Additional continuous secondary efficacy variables, as well as the change from baseline for these variables, will be analyzed either by the MMRM or ANCOVA models described in Section 10.3.1.

Treatment comparisons for the proportion of patients with HbA1c $< 7.0\%$ and $\leq 6.5\%$ will be analyzed using a longitudinal logistic regression with repeated measurements conducted by a generalized linear mixed model including independent variables of treatment, baseline HbA1c value, visit, baseline HbA1c by visit interaction, and treatment by visit interaction. An unstructured covariance structure will be used. As a sensitivity analysis, the proportion of patients with HbA1c $< 7.0\%$ and $\leq 6.5\%$ at Week 26 (Visit 18), imputed using LOCF, will be compared using a logistic regression model including treatment and baseline HbA1c value in the model.

Actual and change from baseline in basal, prandial, and total dose, as well as the prandial/total insulin dose ratio, will be analyzed by the MMRM models described in Section 10.3.1.

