### 5.2. Determination of Sample Size

Patients will be randomized in a 2:1 ratio to LY900014 and insulin lispro, both administered 0 to 2 minutes before meals. Assuming a non-inferiority margin (NIM) of 0.4%, no true difference between treatment arms, and an SD of 1.1%, 480 completers (320 in the LY900014 group and 160 in the insulin lispro group) will provide 96% power to show noninferiority between LY900014 and insulin lispro using the upper limit of a 2-sided 95% confidence interval (CI; LY900014 – insulin lispro). Assuming a 15% dropout rate for 26 weeks, approximately 564 patients will need to be randomized.

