**Table 6.2. Baseline and Post-Baseline Definitions and Patient Population by Study Period and Type of Analysis**

Study Period/Analysis	Patient Population	Baseline Observations	Post-Baseline Observations
Lead-In Period			
TEAEs	All Enrolled Patients	Prior to first dose of open-label insulin lispro (or Visit 2 date if the dose date is missing)	The entire lead-in period after first dose of open-label insulin lispro and prior to the first dose of IP (or Visit 8 date if the dose date is missing).
Basal, prandial, and total insulin doses, and prandial/total insulin dose ratios continuous analysis	All Randomized Patients	Visit 2	Visits 3 to 8 prior to initiation of IP
Weight MMRM and ANCOVA	All Randomized Patients	Last of Visits 1-2	Visits 3–8 AND Last of Visits 3-8
26-Week Treatment Period (including Safety Follow-Up Visit where applicable)			
HbA1c MMRM and ANCOVA	All Randomized Patients with a baseline and at least 1 post-baseline observation while on IP	Last of Visits 7-8	Visits 11, 13, 15, and 18 prior to discontinuation of IP AND Last of Visits 9-18 prior to discontinuation of IP
HbA1c categorical analyses longitudinal logistic regression and LOCF logistic regression	All Randomized Patients with a baseline and at least one post-baseline observation while on IP	Last of Visits 7-8	Visits 11, 13, 15, and 18 prior to discontinuation of IP AND Last of Visits 9-18 prior to discontinuation of IP
1-hr and 2-hr PPG and other MMTT variables	All Randomized Patients with a post-baseline observation while on IP	Visit 8 prior to initiation of IP	Visit 18 prior to discontinuation of IP
10-point SMBG, basal, prandial insulin doses, prandial/total insulin dose ratios	All Randomized Patients with a baseline and at least one post-baseline observation	Visit 8 prior to initiation of IP	Visits , 15, and 18 prior to discontinuation of IP AND Last of Visits 9-18 prior to discontinuation of IP

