### **6.11.2. Analyses of Multiplicity Adjusted Objectives**

[figure not shown]
A graphical approach for multiple comparisons (Bretz et al. 2011) will be used to strongly control the overall Type I error (2-sided alpha level of 0.05) for testing the treatment effect for the primary and the following multiplicity adjusted objectives: superiority of LY900014 compared with insulin lispro for (H2) 1-hour postprandial plasma glucose (PPG) excursion at the study primary endpoint, (H3) 2-hour PPG excursion at the study primary endpoint, and (H4) change from baseline to the study primary endpoint in HbA1c.

The graphical testing scheme for this study is displayed in [Figure 6.1](#). All the hypotheses are connected by lines with arrowheads indicating the directions of testing paths. The initial allocation of study total alpha for each hypothesis is located within the same node of the hypothesis. In this study, the study total alpha level (0.05) will be all used for the primary objective (H1) in the initial step. Then, the study total alpha level (0.05) will be allocated to other objectives according to the values of transition weights shown above the connecting lines in the figure once H1 is met. If 1 of the remaining objectives is successfully demonstrated with the given alpha level, its alpha will be allocated to the rest of objectives by the transition weights in the paths. The iterative test procedure continues until none of the remaining objectives can be demonstrated with their preserved alphas or all objectives are demonstrated successful.

An ANCOVA model with strata (country, type of basal insulin during the lead-in period, number of prandial doses at study entry, and HbA1c stratum) and treatment as fixed effects and baseline as a covariate will be used to analyze the 1-hour and 2-hour PPG excursions for all the

randomized subjects with data collected prior to discontinuation of IP. However, if the percentage of the patients with missing MMTT data at baseline is higher than 15%, a constrained longitudinal data analysis model (Liu et al. 2009; Lu 2010) will be used instead.

The superiority testing on change from baseline to the study primary endpoint in HbA1c will be assessed by the same analysis used for the primary objective. The analyses are described in Section 6.11.1. If the p-value is less than the alpha level allocated by the graphical approach, the superiority of LY900014 to insulin lispro will be achieved.

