Sensitivity analysis for PPG excursions may be performed to exclude patients whose PPG excursion could be affected by factors including MMTT consumption amount (for example, partial MMTT was consumed) and correction bolus insulin usage. A summary of the MMTT consumption and bolus insulin dose at baseline and Week 26 will be provided.

Treatment comparisons for the proportion of patients with HbA1c  $< 7.0\%$  and  $\leq 6.5\%$  will be analyzed using a longitudinal logistic regression with repeated measurements conducted by a generalized linear mixed model including independent variables of treatment, baseline HbA1c value, visit, baseline HbA1c-by-visit interaction, and treatment-by-visit interaction. An unstructured covariance structure will be used. As a sensitivity analysis, the proportion of patients with HbA1c  $< 7.0\%$  and  $\leq 6.5\%$  at Week 26 (Visit 18), imputed using LOCF, will be compared using a logistic regression model with terms for treatment and baseline HbA1c value.

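### The primary HbA1c MMRM uses one baseline coefficient for Weeks 4, 8, 12 and 26; a baseline-by-visit term would protect the precision of the Week 26 contrast at almost no cost

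*SAP*

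**What the plan says.** SAP 6.11.1 fits an MMRM to change in HbA1c with unstructured covariance and Kenward-Roger degrees of freedom. Its fixed effects are treatment, three strata (country, basal insulin, number of prandial doses), "visit, and treatment-by-visit interaction, as well as the continuous, fixed covariates of baseline value". The Protocol gives the same list in the synopsis and in 10.3.1: "visit, and treatment-by-visit interaction, as well as the continuous, fixed covariate of baseline value". Neither document has a baseline-by-visit term.

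SAP Table 6.2 takes the HbA1c outcomes from "Visits 11, 13, 15, and 18 prior to discontinuation of IP". The Schedule of Activities puts these visits at Weeks 4, 8, 12 and 26.

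The Week 26 contrast decides H1. For H4, SAP 6.11.2 says that superiority "will be assessed by the same analysis used for the primary objective". Protocol 10.3.3.2 says that HbA1c at all time points "will be analyzed by the same MMRM model used for the primary analysis".

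Two other HbA1c models treat baseline differently:
- The longitudinal logistic model for HbA1c <7.0% and ≤6.5% (SAP 6.11.5) includes "baseline HbA1c value, visit, baseline HbA1c-by-visit interaction, and treatment-by-visit interaction".
- The secondary ANCOVA in SAP 6.11.3 models the Week 26 endpoint alone, with LOCF, and so estimates its own baseline slope.

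**The concern.** The four visits fall in different phases. Protocol 5.4 describes a "12-week intensive titration period to optimize prandial insulin dosing followed by a 14-week maintenance period". Weeks 4 and 8 lie inside titration, Week 12 closes it, and Week 26 follows 14 weeks of maintenance. Change at Week 4 could well depend on baseline less strongly than change at Week 26. This is plausible, but the documents do not show it.

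If the slopes do differ, the fitted common slope is a compromise that leans towards the visits with the smallest residual variance, which may be the early ones. The part of the Week 26 baseline effect that the common slope misses stays in the residual and widens the Week 26 confidence interval. At stake is some precision in the one contrast that serves both H1 and H4.

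**Working it through.** **Inputs from the documents** (SAP 5.2): margin 0.4, true difference 0, and "an SD of 1.1%, 480 completers (320 in the LY900014 group and 160 in the insulin lispro group) will provide 96% power", judged by the upper limit of a two-sided 95% CI. There are four visits, so the extra term costs 4 − 1 = 3 df.

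**Inputs that are assumptions**, because the documents give none: the baseline slope at each visit, baseline SD 0.7 to 1.0, between-visit correlation 0.5 to 0.8 (autoregressive or exchangeable), and Week 4 residual SD of 0.45, 0.6, 0.8 or 1.0 times that at Week 26. The Week 26 residual SD is set to the planning value of 1.1.

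**Step 1: the plan's own figure.** SE = 1.1 × √(1/320 + 1/160) = 0.1065. Power = Φ(0.4/0.1065 − 1.96) = Φ(1.796) = 96.4%, which agrees with the stated 96%. The CI half-width is 1.96 × 0.1065 = 0.209.

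**Step 2: effect of a common slope, complete data.** Let β be the visit slopes, b the common slope, s the Week 26 residual SD and SDx the baseline SD. Then b = 1′S⁻¹β / 1′S⁻¹1 with S = Σ + SDx²(β − b1)(β − b1)′, iterated to convergence, and

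SE ratio = √(1 + (β₂₆ − b)² SDx² / s²).

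For example, a gap |β₂₆ − b| of 0.4 with SDx = 1.0 gives √(1 + 0.16/1.21) = 1.064.

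| Gap | SE ratio (SDx 0.7 to 1.0) | H1 power |
|---|---|---|
| 0.1 | 1.002 to 1.004 | 96.3 to 96.2% |
| 0.2 | 1.008 to 1.016 | 96.1 to 95.9% |
| 0.3 | 1.018 to 1.037 | 95.8 to 95.2% |
| 0.4 | 1.032 to 1.064 | 95.4 to 94.2% |

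**Step 3: a grid of 128 settings per slope pattern, complete data.**

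| Slopes at Weeks 4/8/12/26 | SE increase: median (range) | H1 power: median (lowest) |
|---|---|---|
| Equal, −0.40 | 0% | 96.4% |
| Mild, −0.30/−0.36/−0.41/−0.45 | 0.4% (0.1 to 1.7%) | 96.3% (95.8%) |
| Moderate, −0.20/−0.32/−0.42/−0.50 | 1.5% (0.4 to 6.6%) | 95.9% (94.1%) |

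Under moderate drift the half-width goes from 0.209 to 0.212 at the median and 0.223 at most. In completers, 480 × (1 − 1/1.015²) ≈ 14 at the median and 480 × (1 − 1/1.066²) ≈ 58 at worst.

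**Step 4: simulation with dropout.** 600 trials per case, 564 patients randomized 2:1, about 14% monotone dropout depending on the previous change.

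| Case | Mean SE without term | Mean SE with term | Ratio |
|---|---|---|---|
| Equal | 0.1040 | 0.1040 | 1.000 |
| Mild | 0.1044 | 0.1039 | 1.004 |
| Moderate | 0.1053 | 0.1038 | 1.015 |
| Moderate, worst setting | 0.1067 | 0.1006 | 1.061 |

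The worst setting is Week 4 SD ratio 0.45, exchangeable correlation 0.8 and baseline SD 1.0. H1 power there is 96.3% without the term and 97.8% with it. The empirical SDs differ less than the model SEs: ratio 1.009 for moderate drift and 1.032 at the worst setting.

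**Step 5: a steeper pattern, outside the grid.** Slopes of −0.10/−0.25/−0.35/−0.50 with small early SDs, correlation 0.8 and baseline SD 1.0 give an SE ratio of 1.094 and 93.0% power with complete data. Simulated with about 15% dropout, following the same mechanism in both arms, the SE is 0.1124 without the term and 0.1033 with it, and power is 93.5% and 95.8%.

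**Step 6: bias.** Under a true difference of 0, the mean estimate in Step 4 was within 0.005 of zero for both models. In the second set of simulations, with the same dropout mechanism in both arms, it was at most 0.007 from zero. The Monte Carlo SE is about 0.104/√600 = 0.004. Bias appeared only when dropout was made to depend on baseline in opposite directions by arm and slopes differed: 0.0225 and 0.0520 HbA1c points with the common slope, against −0.0010 and 0.0019 with the interaction.

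**The case against.** The strongest reply is that this is a modelling preference. A common baseline slope in a pre-specified MMRM is a valid choice under randomization, Protocol and SAP agree on it, and a wider CI is conservative for non-inferiority. Nothing in the documents shows that slopes differ, and with equal slopes the loss is zero. The SD of 1.1 is not tied to either model; if it already describes the common-slope residual, planned power stays 96.4% and the term could only narrow the CI. The lowest grid power, 94.1%, comes from a complete-data formula scaled to 480 completers. The MMRM also uses partial data from other randomized patients, and with dropout simulated at that setting the SE is 0.1067, practically the planning value. The ANCOVA in 6.11.3 already has its own Week 26 slope.

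Most of this stands, and it limits the size of the point. It does not show a downside to adding the term: the simulated SE is the same to four decimals when slopes are equal. The ANCOVA is no substitute, because it uses LOCF, is secondary, and decides neither H1 nor H4.

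A reader might infer that the SAP contradicts itself, since its HbA1c-target model has the interaction. It does not: that is a logistic mixed model on another scale, so it is a precedent only.

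**Conclusion.** The point holds as an efficiency improvement worth considering, conditional on slopes that differ by visit. Under the assumed drifts the Week 26 SE is about 0.4% (mild) to 1.5% (moderate) larger at the median, and 6.6% larger in the worst grid setting. These sizes rest entirely on assumed slopes, baseline SD and correlations.

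Three stronger readings are not supported:
- **That the 96% power is wrong.** It reproduces from the plan's own inputs, and simulated power at the worst grid setting is 96.3% without the term. Only the steeper pattern outside the grid gave about 93%.
- **That the primary estimate is biased.** None appeared beyond simulation error when dropout followed one mechanism in both arms. The 0.02 to 0.05 points required dropout related to baseline in opposite directions by arm, which nothing in the documents indicates.
- **That power for H4 is lost by some stated amount.** The documents give no H4 effect size, so only a possibly wider CI can be shown.

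**What to change.** Before unblinding, add baseline HbA1c-by-visit as a fixed effect to the primary HbA1c MMRM in SAP 6.11.1, matching the term already in the HbA1c-target model of 6.11.5. The model has no treatment-by-baseline term, so the Week 26 contrast keeps its meaning.

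Carry the term into the analyses that reuse this model:
- H4 (6.11.2)
- the Per Protocol and Completer repeats (6.11.3)
- HbA1c over time (6.11.5; Protocol 10.3.3.2)
- HbA1c by antibody status (6.12.7.1)
- the HbA1c subgroups (6.13.1), except the HbA1c-stratum subgroup, where the SAP drops continuous baseline
- the COVID-19 sensitivity analysis (7.6)

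The cost is 3 degrees of freedom among about 550 patients, and SAP wording. Protocol 10.3.1 requires an amendment only for a change to a principal feature. If the sponsor counts the primary model as one, the synopsis and 10.3.1 need amending as well.
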